## **8. Statistical Considerations**

### **8.1. Statistical and Analytic Plans**

8.1.1. All statistical methods will be based on the International Conference on Harmonization (ICH) E9 document "Statistical Principles for Clinical Trials".

### **8.2. Hypotheses –**

#### **8.2.1. Part 1 is exploratory**

##### **8.2.1.1. Primary Endpoint**

8.2.1.1.1. Percentage of subjects reporting suboptimal adherence to ART therapy on the MAAS. Optimal adherence is measured as a score of 90% or better on Rasch score.

##### **8.2.1.2. Secondary Endpoints**

8.2.1.2.1. To assess the psychometric properties of the Midland ART Adherence Survey. We will employ a Rasch statistical approach. Rasch Analysis (RA) is a unique approach of mathematical modeling based upon a latent trait and accomplishes stochastic (probabilistic) conjoint additivity (conjoint means measurement of persons and items on the same scale and additivity is the equal-interval property of the scale).

8.2.1.2.2. Identify and classify the case mix or heterogeneity of subjects who report suboptimal and optimal adherence. Optimal adherence is measured as a Rasch score of better than

90% on the Midland AD Adherence scale. Suboptimal is any score 90% or below. Rasch scores range from 0% (no adherence) to 100% (perfect adherence).

### 8.2.2. Part 2

#### 8.2.2.1. Primary Endpoint

8.2.2.1.1. Percentage of subjects reporting suboptimal adherence, analyzed by intention to treat, from baseline to 16 weeks.

8.2.2.1.1.1. *We hypothesize that a minimum of 85% of subjects taking DRV/COB/FTC/TAF will demonstrate an optimal adherence score from baseline to four-months as measured by the Midland ART Adherence Survey.* Optimal adherence is defined as a Rasch score greater than or equal to 90%. Rasch scores range from 0% (no adherence) to 100% - (perfect adherence).

8.2.2.2. Secondary Endpoints. These are descriptive endpoints so no hypotheses are tested.

8.2.2.2.1. Change at 4 months from baseline in tolerability measured by standardized patient reported outcome questionnaire

8.2.2.2.2. Percentage of subjects with greater than or equal to 90% by pill count

8.2.2.2.3. Proportion of subjects that have HIV-1 RNA  $\geq 50$  copies/mL at baseline and at month 4

8.2.2.2.4. Proportion of subjects with significant changes at 4 months from baseline in serum creatinine, AST or ALT

8.2.2.2.5. Change at 4 months from baseline in absolute and percentage CD4.

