#### 3.2.1. Primary Objectives

3.2.1.1. To determine potential changes in ART adherence in subjects who report suboptimal adherence due to side effects from integrase containing regimens switching to Symtuza.

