#### 4.2.1. Primary Endpoint:

4.2.1.1. Change in adherence from baseline to 4 months, measured by adherence surveys

#### 4.2.2. Secondary Endpoints:

4.2.2.1. Change at 4 months from baseline in tolerability measured by standardized patient reported outcome questionnaire

4.2.2.2. Proportion of subjects that have HIV-1 RNA  $\geq$  50 copies/mL at baseline and at Week 16

4.2.2.3. Proportion of subjects with significant changes at 4 months from baseline in serum creatinine, AST or ALT

4.2.2.4. Change at 4 months from baseline in absolute and percentage CD4.

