**8.4. Description of Statistical Methods****8.4.1. General Approach**

8.4.1.1. When a trial is designed so that more than one study endpoint or comparison could lead to a conclusion that effectiveness was established, testing each endpoint separately at alpha 0.05 will inflate the Type I error rate and overstate the statistical significance. Therefore, we will use the primary endpoint from Part 2 as our measure at the 0.05 level to reduce the potential for a Type I error rate.

8.4.1.2. After the data have been cleaned, we will examine the distribution and dispersion of data through descriptive numerical summaries and graphical tools such as scatter plots and box plots, probability plots, scatter matrix plots, co-plots, and trellis graphics to assess distributional assumptions and relationships among important variables. Before attempting a longitudinal analysis of the change in our outcomes using a mixed, generalized linear model, we will use profile plots, empirical summary plots and correlograms to guide us in the formulation of our model.

8.4.1.3. All data will be summarized. For baseline characteristics and safety outputs a total overall column will be included to summarize all subjects. Where appropriate, data will be summarized by visit. In summary tables of continuous variables, the minimum and maximum statistics will be presented to the same number of decimal places as the original data. The arithmetic mean (AM), median, 95% confidence interval (CI), standard deviation (SD) and standard error (SE) will be presented to one more decimal place than the original data.

8.4.1.4. In summary tables of categorical variables, counts and percentages will be used. In non-parametric summaries and analyses the minimum and maximum will be presented to the same number of decimal places as the original data. The mean, median, lower and upper quartiles will be presented to one more decimal place than the original data. The median difference and 95% CI will only be presented in statistical analysis outputs.

8.4.1.5. Preliminary analyses will examine descriptive and clinical characteristics at baseline. Stata (Version 16.1) and R (version 3.6.0) statistical packages will be used for all data analysis.

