## 8.6. Part 2 –

### 8.6.1. Primary Endpoint

- 8.6.1.1. Percentage of subjects reporting suboptimal adherence, analyzed by intention to treat, from baseline to four-months using Rasch scores. The hypothesis testing will be carried out at the 5% (2-sided) significance level unless otherwise specified. P-values will be rounded to three decimal places. P-values less than 0.001 will be reported as <0.001 in tables. P-values greater than 0.999 will be reported as >0.999.
- 8.6.1.2. We hypothesize that a minimum of 85% of subjects taking DRV/COB/FTC/TAF will demonstrate optimal adherence from baseline to four-months as measured by the Midland ART Adherence Survey. Optimal adherence is defined as a Rasch score greater than or equal to 90%. Rasch scores range from 0% (no adherence) to 100% (perfect adherence).

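### Part 2 primary endpoint: sections 3 and 4 define a change from baseline, section 8 hypothesises a fixed 85% level, and the two-sided 5% test is tied to neither

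*Protocol*

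**What the plan says.** Protocol 3.2.1.1 gives the Part 2 primary objective as "To determine potential changes in ART adherence in subjects who report suboptimal adherence" because of side effects, once they switch regimen. Endpoint 4.2.1.1 matches it: "Change in adherence from baseline to 4 months, measured by adherence surveys".

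Section 8 describes something else. The primary endpoint in 8.2.2.1.1 is "Percentage of subjects reporting suboptimal adherence, analyzed by intention to treat, from baseline to 16 weeks", and 8.6.1.1 repeats it with four months in place of 16 weeks. The hypothesis in 8.2.2.1.1.1 is that "a minimum of 85% of subjects taking DRV/COB/FTC/TAF will demonstrate an optimal adherence score from baseline to four-months", and 8.6.1.2 says again that "a minimum of 85% of subjects taking DRV/COB/FTC/TAF will demonstrate optimal adherence from baseline to four-months". Optimal means a Rasch score of 90% or more on the Midland ART Adherence Survey (MAAS).

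On testing, 8.6.1.1 states: "The hypothesis testing will be carried out at the 5% (2-sided) significance level unless otherwise specified". Section 8.4.1.1 handles multiplicity by resting on this endpoint alone: "we will use the primary endpoint from Part 2 as our measure at the 0.05 level". Part 1 is labelled exploratory (8.2.1) and the Part 2 secondary endpoints carry no hypotheses (8.2.2.2, 8.7.1).

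**The concern.** A change from baseline and a level of 85% have different null hypotheses. Under the first, the null is that the proportion optimal is the same at baseline and Week 16. Under the second, it is that the Week 16 proportion equals 85%, whatever the baseline was. The protocol promises one two-sided 5% test and never says which null it addresses.

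The phrase about running from baseline to 16 weeks does not settle it. In 8.2.2.1.1 it could be read as a change in a percentage, but 8.2.2.1.1.1 uses nearly the same phrase for an absolute level.

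This endpoint is the protocol's whole protection against false-positive claims. In an open single-arm study, an unstated null can be chosen after the results are known. If the two nulls usually gave the same answer this would be a drafting matter, so the check below asks how often they disagree.

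**Working it through.** **Inputs.** n = 30 (6.2.2.1, 8.8.2); optimal is a Rasch score of 90 or more (8.6.1.2); reference level 0.85 (8.6.1.2); two-sided alpha 0.05 (8.6.1.1).

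**Assumptions.** The protocol names no primary test, so I use exact McNemar for change and exact binomial for level. There is no dropout. Baseline optimal is first taken as 0/30, because entry requires reporting more than 2 missed doses a month (6.2.3.1.1.2). Entry is not defined by the Rasch score, so this is varied below.

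**The plan's own figure.** Section 8.8.2 gives n = ln(1 − 0.95)/ln(1 − 0.10) = ln(0.05)/ln(0.90) = 28.43, which rounds up to 29; the protocol states 30. This is the number needed to see at least one event occurring at a 10% rate. It does not show which test was intended, because it matches neither.

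**Change test.** With x subjects becoming optimal and none worsening, p = 2 × 0.5^x. For x = 5, p = 0.0625; for x = 6, p = 0.031. Six of 30 is enough.

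**Level test against 0.85.** Two-sided exact p-values, by the minimum-likelihood method and by doubling the smaller tail:

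| Optimal at Week 16 | Minimum-likelihood | Doubled tail |
|---|---|---|
| 18/30 | 0.0008 | 0.0016 |
| 20/30 | 0.0097 | 0.0193 |
| 21/30 | 0.0354 | 0.0556 |
| 22/30 | 0.118 | 0.140 |
| 26/30 | 1.0 | 1.0 |
| 29/30 | 0.0758 | 0.0961 |
| 30/30 | 0.0173 | 0.0153 |

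**The two tests together, baseline 0/30.**

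- 6/30 to 20/30: significant improvement (p at most 0.031) and significantly below 85% (p at most 0.019).
- 21/30: change succeeds; the verdict against 85% depends on the exact method.
- 22/30 to 25/30: change succeeds; the observed level (73% to 83%) misses 85%, not significantly.
- 26/30 to 29/30: change succeeds and the observed level meets 85%, but the test does not reject 85%.
- 30/30: the only result that rejects 85% upward. Its probability is 0.90^30 = 0.04 if the true rate is 90% and 0.95^30 = 0.21 if it is 95%.

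**Sensitivity to baseline.**

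- Baseline 5/30, nobody worsens: 6 improvers are needed, so the conflict band is 11/30 to 20/30.
- Baseline 5/30, least favourable pairing (all five worsen): 15 v 5 gives p = 0.041 and 14 v 5 gives p = 0.064, so the band is 15/30 to 20/30.
- Week 16 result 20/30, least favourable pairing: baseline 8/30 (20 v 8) gives p = 0.036 and baseline 9/30 (20 v 9) gives p = 0.061. The conflict survives any pairing up to 8/30 at baseline.
- Week 16 result 20/30, nobody worsens: baseline 14/30 (6 v 0) gives p = 0.031 and baseline 15/30 (5 v 0) gives p = 0.0625. The conflict survives up to 14/30.

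**The case against.** The strongest reply is that section 8 contains only one Part 2 hypothesis, the 85% level, and repeats it directly after the testing sentence. On that reading the test addresses 85%, no null of no change is ever written down, and only the labels in sections 3 and 4 are out of step. A SAP that is not shown might also name the test and the null value.

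The 85% reading is indeed the likelier one for section 8 taken alone. It still leaves the primary objective and the section 4 primary endpoint without a test, and a SAP cannot remove a contradiction between two sections of the protocol. Naming the test may properly be left to a SAP; deciding what the primary endpoint is may not.

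Section 8.4.1.2 mentions a mixed generalized linear model for change in the outcomes. It appears as something to follow exploratory plots and is not linked to the primary endpoint or to 85%, so it does not resolve the question.

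Three further points stand as qualifications:

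- The 26/30 to 29/30 band reflects low power of the level test at n = 30 more than a conflict between nulls. The conflict proper is 6/30 to 20/30.
- Subjects are selected for poor answers on the same survey, so regression to the mean favours rejecting a null of no change. A significant change in this single-arm design is weak evidence that the switch caused it.
- Because the cohort is chosen as non-adherent, a Week 16 level already says something about change. The benchmark still differs greatly: near 0% in one case, 85% in the other.

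**Conclusion.** The point holds and must be fixed. The protocol gives its single alpha-bearing endpoint two incompatible meanings and does not say which one is tested. Under the stated assumptions, 15 of the possible results (6/30 to 20/30) count as success on one reading and as significant failure on the other. The exact width of that band depends on the assumed tests, the absence of dropout and the baseline proportion, but the conflict remains with several subjects already optimal at baseline. The contradiction itself rests on the text alone and needs none of these assumptions.

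A separate, minor slip: 8.2.1.2.2 says "Suboptimal is any score 90% or below", while 8.2.1.1.1, 8.5.1.1, 8.2.2.1.1.1 and 8.6.1.2 count exactly 90% as optimal. It concerns a Part 1 secondary endpoint and does not add to the severity.

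**What to change.** State one endpoint and one null, in identical words, in 4.2.1.1, 8.2.2.1.1 and 8.6.1.1.

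- **Preferred, because it matches objective 3.2.1.1 and keeps the protocol's dichotomy:** change from baseline to Week 16 in the proportion of enrolled subjects with a MAAS Rasch score of 90 or more; null hypothesis of no change; paired exact (McNemar) test, two-sided 5%. Keep 85% in 8.2.2.1.1.1 and 8.6.1.2 as the expected Week 16 level, reported as percent optimal with an exact 95% confidence interval and no separate test. A paired test on the 0 to 100 score would also fit the objective. The report should acknowledge regression to the mean.
- **Alternative:** keep the 85% level as primary, write its null explicitly, and reword 3.2.1.1 and 4.2.1.1 to match. At n = 30 only 30/30 would reject upward, so the sample size would have to be reconsidered.

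In either case, correct 8.2.1.2.2 so that 90% or better is optimal and below 90% is suboptimal.

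The preferred option costs a wording amendment only. The survey is already scheduled at the screening or combined visit and at Week 16 (Table 6.2.4.1.2), so no new data, visits or patients are needed. At n = 30, with none optimal at baseline and none worsening, the change test has 57% power if 20% become optimal and 92% if 30% do. The 85% option carries the further cost of a new sample-size justification and probably more subjects.

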8.2.2.2.6. Change at 4 months from baseline in weight

8.2.2.2.7. Number of drug discontinuation for any reason

### 8.3. Analysis Datasets

#### 8.3.1. Demographic:

8.3.1.1. This dataset contains all subjects' demographic data (i.e., Age, Race, and Gender), disposition data (i.e., Date patient withdrew from the study), and key dates such as date of first dose, date of last collected Case Report Form (CRF) and duration on treatment. The dataset has the format of one observation per subject.

#### 8.3.2. Laboratory:

8.3.2.1. This dataset contains all subjects' laboratory data, in the format of one observation per subject per test code per visit per accession number. Here, we derive the study visits according to the study window defined in the SAP, as well as re-grade the laboratory toxicity per protocol. If the laboratory data are collected from multiple local lab centers, this analysis dataset will also centralize the laboratory data and standardize measurement units by using conversion factors.

#### 8.3.3. Intent-to-Treat:

8.3.3.1. This dataset contains derived primary and secondary endpoint variables from all subjects initially enrolled in the study. This dataset has the format of one record per subject per analysis period.

#### 8.3.4. Modified-Intent-to-Treat:

8.3.4.1. This dataset contains derived primary and secondary endpoint variables from all subjects who took one dose of the treatment medications. This dataset has the format of one record per subject per analysis period.

#### 8.3.5. Vital Sign:

8.3.5.1. This dataset contains all subjects' vital signs collected during the trial. This dataset has the format of one observation per subject per vital sign per visit, similar to the structure for the laboratory analysis dataset.

#### 8.3.6. Adverse Event:

8.3.6.1. This dataset contains all adverse events (AEs) reported including serious adverse events (SAEs) for all subjects. A treatment emergent flag, as well as a flag to indicate if an event is reported within 30 days after the subject permanently discontinued from the study, will be calculated. This dataset has a format of one record per subject per adverse event per start date.

**8.3.7. Medication:**

8.3.7.1. This dataset contains the subjects' medication records including concomitant medications and other medications taken either prior to the beginning of study or during the study. This dataset has a format of one record per subject per medication taken per start date. Incomplete and missing medication start or stop dates will be imputed using instructions defined in the SAP.

**8.3.8. Safety:**

8.3.8.1. This dataset contains data with one record per subject per analysis period to capture safety parameters for all subjects.

**8.4. Description of Statistical Methods****8.4.1. General Approach**

8.4.1.1. When a trial is designed so that more than one study endpoint or comparison could lead to a conclusion that effectiveness was established, testing each endpoint separately at alpha 0.05 will inflate the Type I error rate and overstate the statistical significance. Therefore, we will use the primary endpoint from Part 2 as our measure at the 0.05 level to reduce the potential for a Type I error rate.

8.4.1.2. After the data have been cleaned, we will examine the distribution and dispersion of data through descriptive numerical summaries and graphical tools such as scatter plots and box plots, probability plots, scatter matrix plots, co-plots, and trellis graphics to assess distributional assumptions and relationships among important variables. Before attempting a longitudinal analysis of the change in our outcomes using a mixed, generalized linear model, we will use profile plots, empirical summary plots and correlograms to guide us in the formulation of our model.

8.4.1.3. All data will be summarized. For baseline characteristics and safety outputs a total overall column will be included to summarize all subjects. Where appropriate, data will be summarized by visit. In summary tables of continuous variables, the minimum and maximum statistics will be presented to the same number of decimal places as the original data. The arithmetic mean (AM), median, 95% confidence interval (CI), standard deviation (SD) and standard error (SE) will be presented to one more decimal place than the original data.

8.4.1.4. In summary tables of categorical variables, counts and percentages will be used. In non-parametric summaries and analyses the minimum and maximum will be presented to the same number of decimal places as the original data. The mean, median, lower and upper quartiles will be presented to one more decimal place than the original data. The median difference and 95% CI will only be presented in statistical analysis outputs.

8.4.1.5. Preliminary analyses will examine descriptive and clinical characteristics at baseline. Stata (Version 16.1) and R (version 3.6.0) statistical packages will be used for all data analysis.

**8.5. Part 1 –****8.5.1. Analysis of Primary End-Point**

8.5.1.1. The dependent variable is measured on an ordinal scale (Midland ART Adherence Survey). However, employing Rasch analysis we will convert the data to a standardized range from 0 to 100, where 100 is perfect adherence and zero (0) is complete failure to adhere. Using this scale we will examine the proportion of subjects who meet or exceed 90% adherence.

**8.5.2. Analysis of Secondary End-Points**

8.5.2.1. To assess the psychometric properties of the Midland ART Adherence Survey, we will employ six criteria used in the Rasch approach to evaluating rating scale effectiveness. First, a minimum of 10 observations should be in each category. Second, the shapes of the probability curves should be peaked for each category. Third, the average category measures should increase with the rating scale categories. Fourth, the OUTFIT mean square statistics should be less than 1. Fifth, threshold calibrations should increase with rating scale category. Sixth, the category thresholds should be at least 1.4 logits apart and no more than 5 logits apart.

8.5.2.2. Identify and classify the case mix or heterogeneity of subjects who report suboptimal adherence we will use latent class analysis (LCA); which allows us to identify a finite number of latent subgroups and to explore how treatment effect varies across these subgroups. Such person-centered approaches transcend limitations imposed by diagnostic categories and

classify subjects into latent homogenous classes based on similar response patterns. Latent subgroups of subjects are compared with reference to shape (qualitative differences) symptom levels (quantitative differences).

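### The six criteria in section 8.5.2.1 check how answer categories work; they are not built to test for a single trait and cannot by themselves support the one 0-100 Rasch score behind both primary endpoints

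*Protocol*

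**What the plan says.** Protocol section 8.2.1.2.1 lists the psychometric properties of the MAAS as a Part 1 secondary endpoint and bases the model on one trait: "Rasch Analysis (RA) is a unique approach of mathematical modeling based upon a latent trait".

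Section 8.5.2.1 sets out the assessment: "we will employ six criteria used in the Rasch approach to evaluating rating scale effectiveness". It then counts them off: at least 10 observations per category, peaked category curves, average measures that rise with category, an OUTFIT bound ("Fourth, the OUTFIT mean square statistics should be less than 1"), thresholds that rise with category, and thresholds 1.4 to 5 logits apart. The list stops at six.

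Sections 8.2.1.1.1 and 8.5.1.1 (Part 1) and 8.2.2.1.1.1 and 8.6.1 (Part 2) define the primary endpoints by a single 0-100 Rasch score cut at 90%. Section 8.6.1.2 has: "Optimal adherence is defined as a Rasch score greater than or equal to 90" percent. Section 4.2.1.1 words the Part 2 primary endpoint as change measured by adherence surveys and does not name Rasch, so the dependence on the score comes from section 8.

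**The concern.** A single score has its intended meaning only if the scored items share one latent trait. The MAAS (Appendix 1) asks about forgetting (Q1, Q4), not taking medication because of feeling worse or side effects (Q3, Q7), stopping when well (Q6) and how often doses are taken (Q5, Q8-Q10). One trait is an assumption to be tested here. Q8 to Q10 also ask about missed doses over overlapping periods, which invites dependence between items.

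The stake is greatest in Part 2. Sections 6.2.3.1.1.2 and 6.2.4.2.1 select subjects partly on their side-effect answers (Q3, Q7, Q11), and the regimen blamed for those side effects is then switched. If Q3 and Q7 are scored with the frequency items, the total could rise because side-effect answers change while dose-taking does not. Conversely, Q3 asks whether something has ever happened, so a truthful yes may persist after dose-taking improves. The listed criteria are not designed to reveal either.

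**Working it through.** **1. What each criterion examines, and whether it reaches the six yes/no items (Q1, Q3-Q7).**

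| Criterion (8.5.2.1) | Examines | Yes/no items |
|---|---|---|
| 1. At least 10 per category | category counts | applies |
| 2. Peaked curves | category shape | little content: no middle category |
| 3. Rising average measures | category order | applies |
| 4. OUTFIT below 1 | fit, level not stated | applies, but see step 2 |
| 5. Rising thresholds | threshold order | does not apply: one threshold |
| 6. Spacing 1.4 to 5 logits | threshold distance | does not apply: one threshold |

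Only Q8 is printed with more than two ordered categories (seven). Q9 and Q10 are open counts, and Q11 is free text.

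**2. The OUTFIT bound.** The mean square has expected value 1 when the model fits. Requiring every item or category to fall below 1 rejects nearly everything. Requiring only the average to fall below 1 is close to a coin toss in well-behaved one-trait data.

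**3. The plan's sample figure.** Section 8.8.2: ln(1 - 0.95)/ln(1 - 0.10) = ln(0.05)/ln(0.90) = 28.43, rounded up to 29; the plan states 30. Section 8.8.1 applies the same formula to Part 1. Criterion 1 needs 7 x 10 = 70 responses for Q8 alone, so it cannot be met at that minimum.

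**4. Simulation.** The protocol gives no MAAS item data, so all settings are assumptions: N = 500, person SD 1.8 logits, 100 to 200 replicates, partial credit model. The generic layouts have ten four-category items, divided 5+5 or 7+3 between two traits. The MAAS-like layout has six yes/no items, one seven-category item and two four-category items, with Q3 and Q7 on the second trait. A correlation of 1 means one trait.

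| Layout | Correlation | Criteria 1, 2, 3, 5, 6 all met | Criterion 6 met | Average OUTFIT < 1 | Largest item OUTFIT (mean) | First residual eigenvalue |
|---|---|---|---|---|---|---|
| 5+5, thresholds 3.2 apart | 1 | 94% | 100% | 48% | 1.10 | 1.34 |
| | 0.5 | 94% | 100% | 70% | 1.08 | 2.98 |
| | 0 | 96% | 100% | 84% | 1.07 | 4.18 |
| 5+5, thresholds 2.2 apart | 1 | 99% | 99% | 50% | 1.11 | 1.33 |
| | 0.5 | 34% | 34% | 97% | 1.08 | 3.29 |
| | 0 | 0% | 0% | 100% | 1.06 | 4.59 |
| 7+3, thresholds 2.2 apart | 1 | 100% | 100% | 53% | 1.11 | 1.33 |
| | 0.5 | 64% | 64% | 47% | 1.38 | 2.70 |
| | 0 | 0% | 0% | 11% | 1.58 | 3.67 |
| MAAS-like | 1 | 0% | 58% | 16% | 1.47 | 1.38 |
| | 0.5 | 0% | 65% | 0% | 2.01 | 1.55 |
| | 0 | 0% | 16% | 0% | 2.40 | 1.84 |

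Every item below 1: 0% in every row, one-trait data included. In the MAAS-like rows the five criteria fail together whatever the number of traits, because criterion 1 is never met.

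**5. Do the added checks work on the MAAS-like layout?** A generic eigenvalue cut-off of 2 flags 0% of two-trait sets at N = 500. At n = 30 it flags 55% of one-trait sets against 73 to 76% of two-trait sets, so it does not separate them. The Q3-Q7 residual correlation does better. At n = 100 to 300 it exceeded the average inter-item residual correlation by more than 0.2 in 97 to 100% of two-trait runs, against 0 to 8% of one-trait runs. A repeat with the same layout and person SD, a marginal maximum likelihood fit and 100 runs per case gave 87 to 100% against 0 to 3%. The 87% was at n = 100 and correlation 0.5.

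**The case against.** The strongest objection is that the criteria are not blind, and several parts of it stand. With thresholds 2.2 logits apart, a second trait compresses the spacing and criterion 6 often fails. OUTFIT read per item rises with a second trait in the 7+3 and MAAS-like layouts. A reader might infer that a two-trait survey would pass all six criteria, or that the list could never reject one. The documents and the figures support neither: applied to every item, OUTFIT below 1 fails nearly all surveys, including sound ones.

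A reader might also infer that the six criteria are a gate the survey must pass before its score is used. No text makes the score conditional on them, and section 8.2.1 calls Part 1 exploratory. Nor does it follow that a change in the score is not a change in adherence. Q3, Q6 and Q7 themselves ask about not taking doses, and pill counts give a second measure (4.2.2.7, 8.7.1.2).

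A further objection is that dimensionality checks belong in a statistical analysis plan, which sections 8.3.2 and 8.3.7 mention and which is not at hand. That would answer a silent protocol. This one sets a psychometric endpoint, enumerates the criteria for it and stops at six, so the point concerns a stated method that does not support its stated purpose. The latent class analyses (8.5.2.2, 8.7.3) group subjects and do not test items.

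**Conclusion.** The point holds in limited form. The six criteria assess category function. They are not designed to separate a one-trait from a multi-trait survey and may not do so. Two of them do not apply to the yes/no items, and the OUTFIT bound cannot serve as a discriminator as written. They cannot by themselves justify the single score behind both primary endpoints in section 8.

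The size depends on the survey's unknown item properties. At one end, the five category criteria are met about equally often with one trait or two (94% against 94 to 96%). At the other, threshold spacing alone rejects every uncorrelated two-trait set. All of this rests on assumed item thresholds, person spread and item split. It does not show that the MAAS has two traits, only that the planned assessment may be unable to tell.

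**What to change.** In section 8.5.2.1, relabel the six as category-function checks. Add, on the Part 1 data:

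- item-level infit and outfit with a stated two-sided bound around 1, replacing the one-sided bound with no stated level;
- inter-item residual correlations, in particular Q3-Q7 and the pairs among Q8-Q10;
- principal components of the standardised residuals, with the cut-off set by simulation for this item layout and the achieved Part 1 sample;
- person separation reliability.

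State that these are run before Part 2 outcomes are analysed. Part 1 surveys are analysed once enrolment ends (6.1.4.2), while the interim analysis can fall when 10 subjects reach 4 months (6.2.4.1.3). The text should therefore say which data are used if the interim comes first.

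If one dimension is not supported, keep the planned score as primary. Report a pre-specified sensitivity analysis scored on the dose-taking items (Q5, Q8-Q10), rather than redefining the primary item set from the data.

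The cost is modest analysis work on data already to be collected, in R, which section 8.4.1.5 names. The downsides are that the survey may be shown not to support a single score, and that the shorter item set may itself contain dependent items because Q8 to Q10 overlap. At the stated minimum of 30 respondents the component check would say little.
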